## 5.2 Secondary Objectives and Endpoints

Secondary objectives are:

- To establish the subsidence profile of the PINNACLE® Dual Mobility construct; this will be accomplished by determining the mean subsidence at 3 months, 6 months and 1 year as measured with RSA. This endpoint will be compared to historical PINNACLE® data.
- Other RSA measurements (X and Z translations in mm, X, Y, and Z rotations in degrees, and maximal total point motion in mm) at all time points. These endpoints will be compared to historical PINNACLE® data.
- Linear head penetration (in mm) at 6 weeks, 1 year and 2 years. This endpoint will be compared to historical PINNACLE® data.
- Functional and health status will be measured with Harris Hip Score, HOOS Jr. and Forgotten Joint Score (FJS-12) at baseline and 3 months, 6 months and 1 and 2 years post-operative. These endpoints will be compared to historical PINNACLE® data.

## 5.3 Exploratory Objectives and Endpoints

The following will be summarized as exploratory analyses:

4 MAR 2022; Version Rev 3 DSJ-2019-02 Confidential

- Subsidence for subset of Subjects where RSA data was obtained prior to discharge. This endpoint will be compared to historical PINNACLE® data.
- Analyses to examine the correlation of functional and health status outcomes vs. RSA observations may be explored. This endpoint will be compared to historical PINNACLE® data.
- Incidence of intraprosthetic dislocation (IPD)
- Incidence of intraoperative complications

#### 5.4 Safety Endpoints

The type and frequency of serious, non-serious, and device or procedure related Adverse Events across all study intervals will be summarized.

#### 5.5 Device Description

The PINNACLE® Dual Mobility Metal Liner and BI-MENTUM™ ALTRX® Dual Mobility Polyethylene Liner are commercially available in Canada. All PINNACLE® Acetabular Cups, DePuy femoral stems and DePuy modular, femoral heads used in this clinical investigation are commercially available. The PINNACLE® Dual Mobility Metal Liner and Porous-coated PINNACLE Acetabular Cups are intended for cementless applications. Please refer to Table 1 below for implant compatibility. The part numbers allowed by this protocol are listed in Appendix A.

#### PINNACLE® Acetabular Shell

The shells are designed to assemble with the PINNACLE® Dual Mobility metal liner insert.

#### PINNACLE® Dual Mobility Metal Liner

The dual mobility liner is a CoCr device that forms a modular connection with the acetabular shell and serves an articular surface for the polyethylene liner.

#### BI-MENTUMTM ALTRX® Polyethylene Liner

The liner is attached to the femoral head and then the liner/head construct is impacted onto the femoral stem. The BI-MENTUMTM ALTRX® Polyethylene Liner is then reduced into the dual mobility liner.

#### DePuy Femoral Head

Ceramic and metal heads are allowed for this clinical investigation. The inner diameter of the polyethylene liner bearing surface must correspond to the femoral head size. Please note the Biolox Delta TS femoral head +12 is not intended for use with dual mobility liners.

#### DePuy Femoral Stem

A variety of femoral stems may be used in this investigation, however, only those stems with polished necks are indicated for use with the PINNACLE® Dual Mobility construct. Please refer to Table 1 below for a listing and Appendix A for implant part codes.

4 MAR 2022; Version Rev 3 DSJ-2019-02 Confidential Page 14 of 47

Device	Features
PINNACLE® acetabular shells (primary	Size
and revision)	Primary:48-66mm: Revision 54-72mm
	A
	ACCESSOFIES
Ri-MENTUM TM ALTRX ® nolvethylene	Size
(PE) liners	22.225mm head diameter: ø 41-45
(12)	28mm head diameter: ø 47-55
12/14 Femoral heads	M-Spec Metal Heads: 28mm
	• Standard Metal Heads: 22.225mm,
	28mm
	Delta Heads: 28mm
	Delta TS Heads: 28mm
Femoral stems (polished)	Corail AMT Stems
	Corail Cemented Stems
	Corail Revision Stems
	C-Stem AMT Stems
	Actis Stems
	SUMMIT Porous Stems
	SUMMIT Porous HA Stems
	SUMMIT Cemented Stems
	Reclaim Stems
	
 
Tri-lock BPS Stems
 

Table 1. Implants compatible with the PINNACLE® Dual Mobility Liner

## **6 SUBJECT DEFINITION**

This study will include male and female Subjects, aged 21 or older, who are undergoing primary, unilateral THA, revision and who may have, in the opinion of the Investigator, a risk of dislocation in the operative joint. Subjects who do not meet all inclusion criteria or who meet any of the exclusion criteria will be excluded from study consideration and participation. Subjects who meet all entry criteria and are properly consented may be excluded from further participation due to study withdrawal, see Section 10 for details.

#### 6.1 Inclusion Criteria

Subjects meeting all the following specific criteria will be considered for participation in the study:

4 MAR 2022; Version Rev 3 DSJ-2019-02 Confidential

Page **15** of **47** TV-eFRM-02920

- 1. Individuals requiring THA for:
  - a. a severely painful and/or disabled joint (typically due to non-inflammatory degenerative joint disease).
  - b. failed previous hip surgery.
  - c. or dislocation risks.
- 2. Individuals who are able to speak, read and comprehend the informed patient consent document and willing and able to provide informed patient consent for participation in the study and have authorized the transfer of his/her information to DePuy Synthes.
- 3. Individuals who are willing and able to return for follow-up as specified by the study protocol.
- 4. Individuals who are a minimum age of 21 years at the time of consent.
- 5. Individuals who are willing and able to complete the Subject Hip Outcomes questionnaires as specified by the study protocol.

#### 6.2 Exclusion Criteria

Subjects will be excluded from participation in the study if they meet any of the following criteria:

- 1. Individuals have active local or systemic infection.
- 2. Individuals who have loss of musculature, neuromuscular compromise or vascular deficiency in the affected limb rendering the procedure unjustified.
- 3. Individuals with poor bone quality, such as osteoporosis, where in the surgeon's opinion, there could be considerable migration of the prosthesis or a significant chance of bone fracture and/or the lack of adequate bone to support the implant(s).
- 4. Individuals with Charcot's or Paget's disease.
- 5. Individuals who, in the judgement of the investigator, would not be a candidate for protocol allowable components to be used for their THA.
- 6. Women who are pregnant or lactating.
- 7. Individuals who have had a contralateral hip that was implanted less than 6 months prior to the time of consent into this study or individuals that expect to have a contralateral hip implanted in the 6 months following the time of consent into this study.
- 8. Individuals that have amputations in either leg that would impact rehabilitation following surgery.
- 9. Individuals who are bedridden per the Investigators determination
- 10. Individuals that have participated in a clinical investigation with an investigational product (drug or device) in the last three months.
- 11. Individuals currently involved in any personal injury litigation, medical-legal or worker's compensation claims.

4 MAR 2022; Version Rev 3 DSJ-2019-02 Confidential

- 12. Individuals, in the opinion of the Investigator, who are drug or alcohol abusers or have a psychological disorder that could affect their ability to complete patient reported questionnaires or be compliant with follow-up requirements.
- 13. Individuals diagnosed and taking prescription medications to treat a muscular disorder that limits mobility due to sever stiffness and pain such as fibromyalgia or polymyalgia.
- 14. Subject has a medical condition with less than 2 years life expectancy.
- 15. Individual has a BMI  $\geq$  45 kg/m^2.
- 16. Individuals who require revision arthroplasty and have a well-fixed non-DePuy Synthes femoral stem or a well-fixed DePuy Synthes femoral stem that does not have a polished neck

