#### 6.3 Definition of Subject Enrollment

A patient will be considered enrolled when they have provided signed Informed Consent Document (ICD) to participate in this Investigation, which includes authorization of the release of his/her Protected Health Information (PHI).

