## 8 STUDY PROCEDURES

#### 8.1 **Pre-Operative (-90 days to Day of Surgery)**

Following informed consent and eligibility verification, the Subject will have the following preoperative health and functional status evaluations:

The Subject's orthopaedic medical history and current diagnoses will be documented. Data collected will include but is not be limited to:

- Age, gender, height and weight
- History of concurrent or previous medical issues
- History of previous treatment to the index hip
- Harris Hip Score
- HOOS Jr.
- Radiographs
  - AP Femur\*
  - o Lateral

\*The AP Femur is the preferred view at all time points; however, an AP Pelvis will also be accepted.

The information collected from the 'Pre-Op' visit will be populated on the appropriate eCRFs as indicated in the Time and Events Table (Section 3.2). If pre-operative radiographs of sufficient quality were obtained within 270 days of surgery, then they do not need to be repeated just for the purpose of this study.

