#### 11.4 Interval Windows

Data collected throughout the study will be assessed for compliance with the protocol-specified visit schedule. Six windows are defined based on the number of days prior to or after surgery, Day 0. Visits conducted within the intervals shown in Table 11-1 will be assessed for compliance with the protocol. If multiple visits fall into the pre-operative window, or into the 6 Week post-operative window, the result collected most proximate to surgery will be utilized. If multiple measurements fall into the 3 Month, 6 Month, 1 Year, or 2 Year window, the last value (furthest from surgery) will be utilized for the analysis. All safety data will be included in the Safety analysis.

Study Visit	Study Interval Window (days)	
Pre-Op	-90 to DOS*	
Operative	0	
Prior to Discharge	Day 1 to Discharge	
6 Weeks	28 to 56	

Table 11-1 Study Visit Interval Windows per Time and Events Table

4 MAR 2022; Version Rev 3 DSJ-2019-02 Confidential Page 27 of 47

3 Months	60 to 120
6 Months	135 to 225
1 Year	275 to 455
2 Years	640 to 820

\* For radiographs Pre-Op study film window is from -270 days to date of surgery (DOS).

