#### **11.6.2** Secondary Endpoints

The secondary endpoints are the following:

- RSA measured subsidence (superior cup migration) at 3 months, 6 months and 1 year.
- Other RSA measurements (X and Z translations in mm, X, Y, and Z rotations in degrees, and maximal total point motion in mm) at all time points
- Linear head penetration at 6 weeks, 1 year and 2 years;
- Harris Hip Score at 6 weeks, 3 months, 6 months, 1 year and 2 years;
- HOOS Jr. at 6 weeks, 3 months, 6 months, 1 year and 2 years;
- Forgotten Joint Score (FJS-12) at 6 weeks, 3 months, 6 months, 1 year and 2 years.

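### The forward limb of exclusion 7 runs from consent, not index surgery, so it may cover only about 93 post-operative days and leave 3- and 6-month functional scores open to a planned contralateral THA

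*Combined protocol and SAP*

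**What the plan says.** Exclusion 7 has two limbs, both counted from consent. The backward limb excludes "Individuals who have had a contralateral hip that was implanted less than 6 months prior to the time of consent into this study". The forward limb excludes "individuals that expect to have a contralateral hip implanted in the 6 months following the time of consent into this study". The synopsis (section 3.1) carries the same rule.

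The follow-up clock is different. Section 11.4 states: "Six windows are defined based on the number of days prior to or after surgery, Day 0". Table 11-1 places the 3-month visit on days 60 to 120 and the 6-month visit on days 135 to 225.

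Consent comes first. Section 6.3 says "A patient will be considered enrolled when they have provided signed Informed Consent Document", and section 8.1 orders the steps: "Following informed consent and eligibility verification, the Subject will have the following preoperative health and functional status evaluations". The window for those evaluations opens 90 days before surgery. That limits the visit and not the consent date, and the document sets no maximum interval between consent and surgery.

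Section 11.6.2 lists Harris Hip Score, HOOS Jr. and FJS-12 as secondary endpoints at 6 weeks, 3 and 6 months, and 1 and 2 years. Section 11.12.4 compares them with DSJ_2018_02 by t-test, with a 95% confidence interval for the difference.

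**The concern.** By writing exclusion 7, the sponsor already treats a nearby operation on the opposite hip as a problem for this study. Counting from consent makes the post-operative length of the forward limb depend on how long the patient waits for surgery, which has nothing to do with the construct. The backward limb does not suffer: consent precedes surgery, so it always gives at least six months before the index operation. Only the forward limb is eroded.

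No other rule closes the gap. Contralateral surgery is not among the discontinuation reasons in section 10.1. A Subject who met the criterion as written has not violated the protocol on that account and stays in the Per Protocol set (section 11.5). The analyses in sections 11.12.2 and 11.12.4 have no rule for scores taken after such an operation.

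The handling of repeat visits can add to the exposure. An additional visit within a study interval repeats all three scores (section 8.6), and from 3 months onward "the last value (furthest from surgery) will be utilized for the analysis". A score taken after a contralateral operation can therefore replace one taken before it in the same window.

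At stake is a possible shift in the 3- and 6-month functional means, and in their comparison with the historical cohort, from a cause other than the study device.

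**Working it through.** The plan states no figure on this point. Its one precision figure, 2 x 0.2/√30 = 0.073 mm (section 11.8), reproduces; it concerns the primary endpoint and is not used here.

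**Inputs.** Forward limb: six months from consent (section 6.2). Visit windows: 3 months = days 60 to 120, which is 61 days; 6 months = days 135 to 225, which is 91 days (Table 11-1). Consent-to-surgery interval L: not limited by the document; L = 90 is allowed. Assumption: six months = 183 days, with 180 to 184 as the range.

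**Formulas.**
- Last covered post-operative day = 183 - L.
- First uncovered day d = 184 - L.
- Exposed days in a window from a to b = b - max(a, d) + 1, or 0 if negative. This counts the days on which a visit could follow an allowed planned operation. It is not a probability.

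| L (days) | Last covered day | First uncovered day | 3-month window exposed | 6-month window exposed |
|---|---|---|---|---|
| 0 | 183 | 184 | 0/61 | 42/91 |
| 30 | 153 | 154 | 0/61 | 72/91 |
| 60 | 123 | 124 | 0/61 | 91/91 |
| 90 | 93 | 94 | 27/61 | 91/91 |
| 120 | 63 | 64 | 57/61 | 91/91 |

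At L = 90, the 3-month count is 120 - 94 + 1 = 27 and the 6-month count is 225 - 135 + 1 = 91. The row L = 0 is also the result if the six months were counted from surgery: 225 - 184 + 1 = 42.

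**Thresholds.** The 3-month window is exposed only if 184 - L ≤ 120, so L ≥ 64 (61 to 65 over the range for six months). The whole 6-month window is exposed if 184 - L ≤ 135, so L ≥ 49 (46 to 50).

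**Sensitivity.** With six months as 180 to 184 days and L = 90, the first uncovered day is 91 to 95.

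**Timing.** After an operation on day 94, a 6-month visit falls 135 - 94 = 41 to 225 - 94 = 131 days later.

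**Size of a shift, by assumption.** If k of 30 Subjects score lower by D points at a visit, the mean falls by (k/30) x D. With k = 1 and D = 10 this is 0.33 points; with k = 6 and D = 20 it is 4 points. Neither k nor D is in the documents. The formula also requires each of those k Subjects to have had the second operation before the visit and to be scored while still impaired.

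**The case against.** The strongest reply is that the gap is narrow and the consequence limited. Much of this stands.

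- **Three months.** A reader might infer that 3-month results are generally distorted. They are not: there is no exposure unless consent is about 64 or more days before surgery. Even at 90 days, a visit near day 91 precedes any allowed operation.
- **Six months.** A reader might blame the consent anchor for all of the 6-month exposure. With consent on the day of surgery, 42 of 91 window days are still open, and the 1- and 2-year visits are uncovered under either anchor. The protocol chose a limited exclusion, not full protection.
- **Size and direction.** The documents give no share of staged-bilateral patients, no distribution of waiting times and no effect of an opposite-hip operation on these scores.
- **Site differences and historical comparison.** Unequal effects by site would be conjecture, since no waiting times are given. The eligibility rules of DSJ_2018_02 are not in the documents; if they use the same anchor, both cohorts share the gap.
- **Consequence.** The primary endpoint is motion of the index shell relative to beads in the index acetabulum (section 8.7). The functional scores carry no hypotheses (section 11.6), their confidence intervals are exploratory (section 11.7), and the historical comparison only supports clinical judgement (section 11.12.4).

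One possible reply fails. The population is described as undergoing unilateral THA, but that describes the index procedure. If it barred a later operation on the other side, the forward limb of exclusion 7 would be unnecessary.

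What remains is the mismatch of anchors, the loss of up to 90 days of cover, or more with earlier consent, and the absence of any rule that makes up for it.

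**Conclusion.** The point holds as a modest, inexpensive improvement to secondary endpoints. With consent at day -90 and six months taken as 183 days, the forward limb covers 93 post-operative days instead of 183. A planned contralateral THA from about day 94 is then allowed, and it can affect the functional scores at a late 3-month visit (days 94 to 120) or at any 6-month visit. The part due to the anchor is 27 of 61 window days at 3 months and 91 - 42 = 49 of 91 at 6 months.

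That these scores are actually distorted cannot be concluded from the documents. The shift of about 0.3 to 4 points is an illustration resting on 1 to 6 of 30 Subjects and a 10 to 20 point drop, both assumed. The primary RSA endpoint and the sample size are unaffected.

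**What to change.** 1. In section 6.2 and the synopsis, keep the existing six months but count the forward limb of exclusion 7 from index surgery instead of from consent. This removes the 3-month exposure and reduces the 6-month exposure to 42 of 91 window days. Extending the exclusion to the end of the 6-month window (day 225) would close the rest, but that lengthens the criterion and is a design preference, not a correction.
2. Record the date of any contralateral THA during follow-up. The visit assessments listed in sections 8.4 and 8.5 name no such item, and a planned admission for an unchanged pre-existing condition is not a serious adverse event under section 9.2, so safety reporting may not capture it.
3. In section 11.12.2, add a supportive summary of Harris Hip Score, HOOS Jr. and FJS-12 that omits visits after a contralateral THA. This also covers the 1- and 2-year visits, unplanned operations, and Subjects already enrolled; the COVID-19 replacement wording in section 10.2 suggests there may be some.

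Cost: one reworded criterion in two places, one date field and one extra summary. A few staged-bilateral patients become ineligible. The criterion may then differ from that of DSJ_2018_02, which should be checked before the change is made.

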#### 6.3 Definition of Subject Enrollment

A patient will be considered enrolled when they have provided signed Informed Consent Document (ICD) to participate in this Investigation, which includes authorization of the release of his/her Protected Health Information (PHI).

## 7 STUDY DESIGN

This study is designed as a prospective, multi-center, non-randomized, non-controlled study. This study does not limit the surgical approach involved in the treatment of the Subject as long as the protocol specified products are utilized.

#### 7.1 Subject Enrollment

A minimum of 30, and up to 45, Subjects will be enrolled at 3 Investigational sites. No protocol specified activities can be completed until written Informed Consent is obtained for a Subject. Standard of care radiographs that have been taken prior to consent may be used for the purposes of the protocol as long as they were taken within 270 days of surgery.

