Sample Size	The purpose of this study is to summarize the mean subsidence (superior cup migration) of the acetabular shell as measured with RSA. Mean subsidence will be summarized at all time points; there are no hypotheses in this study. The standard deviation in observed migration values at 2 years post-op is anticipated to be approximately 0.2 mm. Based upon this standard deviation, a sample size of N=30 is anticipated to provide a 95% confidence interval for comparison with historical PINNACLE ® data with a margin of error of approximately $2(0.2/\sqrt{30}) = 0.073$ mm, which is deemed to be an adequate level of precision by the Sponsor. Up to 45 Subjects may be enrolled to offset pre and post-operative attrition.
Statistical Analysis	There are no formal hypothesis tests for this study. Summary statistics of primary, secondary and exploratory outcomes will be provided, along with 95% confidence intervals. Comparisons of the primary and secondary endpoints with historical PINNACLE ® data will be conducted using the t-test and the Fisher's exact test. Those comparisons will only be provided to facilitate clinical judgement.
Interim Analysis	An interim analysis will be conducted when all Subjects have reached 1-year post-op in order to give product development an understanding of acetabular cup subsidence that might be expected for future product development purposes and support regulatory submissions. There is no intention to utilize this interim analysis as a means to justify stopping the study early.
Determination if DMC/CEC	Not Required
Time and Events Schedule	See below

I         I         I>/>         I         I
> > >  >
> >
ļ
$\mathbf{i}$
>
C M/D
>
. >
· >

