#### 8.2 Operative (Day 0)

Each Subject will receive a DePuy femoral stem with a polished neck in combination with a DePuy PINNACLE® acetabular cup. All Subjects will receive a PINNACLE® DM metal liner and a BI-MENTUMTM ALTRX® Dual Mobility Polyethylene Liner. Either metal or ceramic heads may be used; however, compatibilities must align with product labeling. Please note since revisions of existing THAs are acceptable to enroll into this study, variations in what is implanted will occur, however Subjects must receive the PINNACLE® DM metal liner and a BI-MENTUMTM ALTRX® Dual Mobility Polyethylene Liner. If the surgeon determines intraoperatively that there exists insufficient bone quality to support the implantation of the construct that Subject will be withdrawn from the study. Subjects that are withdrawn pre-operatively or intra-operatively will be replaced in order to have a minimum of 30 and up to 45 Subjects implanted with the study devices.

Each surgeon shall perform the surgical approach they are most comfortable with and have the greatest expertise.

Implant sizing shall be performed as per the surgeon's discretion for each individual Subject and will not be standardized between sites. Approximately 5-10 tantalum beads will be placed into the

4 MAR 2022; Version Rev 3 DSJ-2019-02 Confidential Page **20** of **47** TV-eFRM-02920 acetabulum. Bead placement will be standardized across study sites to reduce the possibility of unuseable RSA exams resulting from poor bead spacing or bead occlusion.

Any intra-operative adverse events will be captured as well as details of the surgery and implants/components used. The information collected from the 'Operative' time-point will be populated on the appropriate eCRFs as indicated in the Time and Events Table (Section 3.2).

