#### 10.2 Subject Early Discontinuation

Every Subject should be encouraged to remain in the study until they have completed the protocolrequired 2-year follow-up period. If the Subject discontinues prematurely from the study, the reason for discontinuation must be documented in the source documents and site files and submitted via eCRF.

Data which have been received on Subjects who discontinue prematurely will be included in the analysis of results. Subjects who discontinue prematurely, excluding those withdrawn preoperatively, intra-operatively or those Subjects who were unable to complete their 6 week visit due to the COVID-19 Pandemic, will not be replaced.

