#### 11.7 Levels of Significance

There are no specific hypotheses being tested in this study. To facilitate clinical interpretation, confidence intervals will accompany primary and secondary endpoint estimates and will be 2-sided 95% confidence intervals; these confidence intervals are considered to be exploratory.

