#### 11.8 Sample Size Justification

This study sample size was established to provide adequate precision on the mean subsidence estimate at 2 years. A common standard deviation of 0.2 mm is anticipated. Based upon this standard deviation and a sample size of N=30, a 2-sided 95% confidence interval is anticipated to have a margin of error equal to approximately  $2SE = 2 \times \frac{SD}{\sqrt{n}} = 2 \times \frac{0.2}{\sqrt{30}} = 0.073$  mm. This margin of error was deemed to be an adequate level of precision by the Sponsor.

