#### 11.12 Primary, Secondary, and Safety Endpoint Analyses

#### **11.12.1 Primary Endpoint Analysis**

#### RSA Measured Subsidence at 2 years

The primary endpoint of RSA measured subsidence (Y translation, also known as superior cup migration) results in the 2-year visit window will be summarized on the subset of Subjects in the Per Protocol Analysis Set (primary analysis) who have 6 week and 2 year data for the analysis. The analysis will also be conducted on the subset of Subjects in the Safety Analysis Set (supportive analysis) who have 6 week and 2 year data for the analysis. Standard continuous summaries will be provided along with 95% confidence intervals.

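### The 0.073 mm margin needs 30 analysable subjects at 2 years, but the permitted minimum of 30 enrolled or implanted carries no reserve for attrition

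*Combined protocol and SAP*

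**What the plan says.** **Precision.** Section 11.8 assumes a standard deviation: "A common standard deviation of 0.2 mm is anticipated". The synopsis (section 3.1) agrees: "The standard deviation in observed migration values at 2 years post-op is anticipated to be approximately 0.2 mm". The calculation then runs: "Based upon this standard deviation and a sample size of N=30, a 2-sided 95% confidence interval" has a margin of about 0.073 mm, which the Sponsor accepts as adequate. Neither place includes an attrition term in the calculation.

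**Recruitment range.** Section 7.1: "A minimum of 30, and up to 45, Subjects will be enrolled at 3 Investigational sites". Under section 6.3, a patient is enrolled once consent is signed. Section 8.2 replaces pre-operative and intra-operative withdrawals so as to reach a "minimum of 30 and up to 45 Subjects implanted with the study devices". The synopsis adds that enrolment may go up to 45 to offset losses before and after surgery. It gives no expected loss rate.

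**Replacement.** Section 10.2 sets the rule for "Subjects who discontinue prematurely, excluding those withdrawn preoperatively, intra-operatively" and also excepts those who could not complete the 6-week visit because of COVID-19. Everyone else who discontinues early is not replaced.

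**Analysis population.** The primary analysis (section 11.12.1) is restricted to Per Protocol subjects "who have 6 week and 2 year data for the analysis". Section 11.5 removes subjects with excluding major protocol violations from that set. Section 11.15 rules out imputation.

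**The concern.** The n in the margin formula is the number of subjects who contribute a 2-year migration value. The n in the recruitment rule is the number who consent (section 7.1) or receive the implant (section 8.2). The plan sets both at 30, although losses can occur between them: withdrawal of consent, death, revision of a component (section 10.1), a major protocol violation, or a missing 6-week reference exam or 2-year exam.

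The study has no hypotheses (sections 11.6 and 11.7), so the precision of the interval is the only justification given for the sample size. A trial could comply fully with sections 7.1 and 8.2 and still not deliver the precision on which that justification rests.

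**Working it through.** **Inputs from the documents**
- SD = 0.2 mm (section 11.8, synopsis).
- Two-sided 95% interval (section 11.7).
- n = 30 in the formula (section 11.8).
- Range 30 to 45, enrolled (section 7.1) or implanted (section 8.2).

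**Assumed input.** The documents give no loss rate. I take d = 10%, 20% and 30% of implanted subjects not analysable and not replaced.

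**1. Reproduce the plan's figure.** Margin = 2 × SD/√n = 2 × 0.2/√30 = 0.0730 mm. This agrees with the stated 0.073 mm. The t multiplier with 29 degrees of freedom gives 0.0747 mm at the same n, about 2% more (0.0747/0.0730 = 1.02).

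**2. Look for slack at the floor.** With 29 analysable, 2 × 0.2/√29 = 0.0743 mm. By the plan's formula, 30 is the smallest n that rounds to 0.073 mm, so a single unreplaced loss from 30 already exceeds it.

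**3. Margin when 30 are implanted.** Analysable n = 30 × (1 − d). Widening on the plan's formula = √(30/n) − 1.

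| Assumed loss | Analysable n | 2 × SD/√n (mm) | Widening | t-based margin (mm) |
|---|---|---|---|---|
| 0% | 30 | 0.0730 | – | 0.0747 |
| 10% | 27 | 0.0770 | 5% | 0.0791 |
| 20% | 24 | 0.0816 | 12% | 0.0845 |
| 30% | 21 | 0.0873 | 20% | 0.0910 |

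**4. Margin at the top of the range.** With 45 implanted and no loss, 2 × 0.2/√45 = 0.0596 mm. At 20% loss, 36 remain and the margin is 0.0667 mm. At one-third loss, 30 remain and the margin is 0.073 mm.

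**5. Implanted number that keeps 30 analysable.** 30/(1 − d), rounded up:
- d = 10%: 33.3, so 34.
- d = 20%: 37.5, so 38.
- d = 30%: 42.9, so 43.
- d = one third: 45.

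Every one of these lies within the existing cap.

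**The case against.** The strongest reply is that attrition has been considered. The synopsis ties the increase to 45 to losses before and after surgery, directly after the margin calculation. Because section 8.2 replaces pre-operative and intra-operative withdrawals separately, all 15 places above 30 can absorb post-operative loss if the cap is counted in implanted subjects. At 45 implanted and 20% loss, precision is better than stated. This stands, and it confines the point to the floor of the range.

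The consequence is also small. The margin is described as approximate, no largest tolerable margin is given, and section 11.7 says the intervals "will be 2-sided 95% confidence intervals; these confidence intervals are considered to be exploratory". At 10%, 20% and 30% loss the increase over 0.073 mm is 0.004, 0.009 and 0.014 mm. An SD of 0.2 × √(30/24) = 0.224 mm in place of 0.2 mm would widen the interval as much as losing 20% of subjects. This stands too, and it keeps the severity low.

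A reader might go further in four ways that the documents do not support:
- **That the trial as planned misses its precision.** It does so only if recruitment stops at or near 30 and unreplaced losses follow.
- **That the floor is simply 30 consented patients.** Section 8.2 aims for 30 implanted. The two sections differ in unit, and the text does not say which governs.
- **That the interval is 8% to 25% wider than stated.** That range compares t-based margins after loss (0.0791 to 0.0910 mm) with the plan's 2SE figure, so it mixes a change of multiplier with attrition. Like for like, the widening is 5% to 20%.
- **That section 8.2 predicts unusable RSA exams.** It describes standardised bead placement as a way to make them less likely, and it gives no rate.

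What the reply does not remove is that going above 30 is optional, no loss rate is stated, and nothing requires a number above 30.

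**Conclusion.** The point holds for the minimum design only. The 0.073 mm margin describes 30 analysable Per Protocol subjects with 6-week and 2-year RSA data, and the permitted floor of 30 enrolled or 30 implanted does not secure that number. From 30 implanted, assumed losses of 10%, 20% or 30% give 0.077, 0.082 or 0.087 mm on the plan's formula. The upper end of the range meets the stated precision for losses of up to one third of those implanted.

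The sizes rest on the plan's SD of 0.2 mm and on loss rates that I have assumed. Severity is low: no test or success criterion depends on the margin, and the documents do not show that a margin of 0.08 mm would be inadequate. It is still worth correcting, because this is the only quantitative support for the sample size.

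**What to change.** 1. In section 11.8 and the synopsis, say that 0.073 mm applies to 30 analysable Per Protocol subjects with 6-week and 2-year RSA data, and state the assumed loss rate d.
2. Then do one of the following:
   - report the margin expected at the minimum design, for example 0.082 mm (0.085 mm t-based) if d = 20%; or
   - set the minimum implanted number at 30/(1 − d) within the cap of 45, for example 34 at 10% or 38 at 20%.
3. Use one unit, enrolled or implanted, for the 30 to 45 range in sections 7.1 and 8.2.

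The floor should not be written in analysable subjects. Enrolment is planned over 12 months, and whether a subject is analysable at 2 years is known only after it has closed.

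The cost is wording plus either a slightly less favourable stated margin or a higher floor (4 more implanted subjects at 10%, 8 more at 20%), with the cap unchanged. If recruitment has already ended, the expected margin can still be restated in the separate SAP, which section 11 says will be finalised before database lock.
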